5.2.2 Dose Modification

Every effort should be made to administer study treatments per the planned dosing schedule. Dose modification guidelines for a particular study treatment are to be followed if AEs are assessed as associated or potentially associated with that study treatment.

5.2.2.1 Dose Modification and Toxicity Management Guidelines for Adverse Events Potentially Associated with Pembrolizumab Treatment

Dose modification and toxicity management for immune-related AEs (irAEs) associated with pembrolizumab

Adverse events associated with pembrolizumab exposure may represent an immunologic etiology. These irAEs may occur shortly after the first dose or several months after the last dose of pembrolizumab treatment and may affect more than one body system simultaneously. Therefore, early recognition and initiation of treatment is critical to reduce complications. Based on existing clinical trial data, most irAEs were reversible and could be managed with interruptions of pembrolizumab, administration of corticosteroids, and/or other supportive care. For suspected irAEs, ensure adequate evaluation to confirm etiology or exclude other causes. Additional procedures or tests such as bronchoscopy, endoscopy, or skin biopsy may be included as part of the evaluation. Based on the severity of irAEs, withhold or permanently discontinue pembrolizumab and administer corticosteroids. Dose modification and toxicity management guidelines for irAEs associated with pembrolizumab are provided in [Table 6](#).

Table 6 Dose Modification and Toxicity Management Guidelines for irAEs Associated with Pembrolizumab

General instructions:				

 1. Corticosteroid taper should be initiated upon AE improving to Grade 1 or less and continue to taper over at least 4 weeks. 2. For situations where pembrolizumab has been withheld, pembrolizumab can be resumed after AE has been reduced to Grade 1 or 0 and corticosteroid has been tapered. Pembrolizumab should be permanently discontinued if AE does not resolve within 12 weeks of last dose or corticosteroids cannot be reduced to ≤ 10 mg prednisone or equivalent per day within 12 weeks. 3. For severe and life-threatening irAEs, IV corticosteroid should be initiated first followed by oral steroid. Other immunosuppressive treatment should be initiated if irAEs cannot be controlled by corticosteroids. 				

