Immune-related AEs	Toxicity grade or conditions (CTCAEv4.0)	Action taken to pembrolizumab	irAE management with corticosteroid and/or other therapies	Monitor and follow-up
Pneumonitis	Grade 2	Withhold	
 • Administer corticosteroids (initial dose of 1-2 mg/kg prednisone or equivalent) followed by taper 	
 • Monitor participants for signs and symptoms of pneumonitis • Evaluate participants with suspected pneumonitis with radiographic imaging and initiate corticosteroid treatment • Add prophylactic antibiotics for opportunistic infections
	Grade 3 or 4, or recurrent Grade 2	Permanently discontinue		
Diarrhea / Colitis	Grade 2 or 3	Withhold	
 • Administer corticosteroids (initial dose of 1-2 mg/kg prednisone or equivalent) followed by taper 	
 • Monitor participants for signs and symptoms of enterocolitis (ie, diarrhea, abdominal pain, blood or mucus in stool with or without fever) and of bowel perforation (ie, peritoneal signs and ileus). • Participants with \geq Grade 2 diarrhea suspecting colitis should consider GI consultation and performing endoscopy to rule out colitis. • Participants with diarrhea/colitis should be advised to drink liberal quantities of clear fluids. If sufficient oral fluid intake is not feasible, fluid and electrolytes should be substituted via IV infusion.
	Grade 4	Permanently discontinue		

Immune-related AEs	Toxicity grade or conditions (CTCAEv4.0)	Action taken to pembrolizumab	irAE management with corticosteroid and/or other therapies	Monitor and follow-up
AST / ALT elevation or Increased bilirubin	Grade 2	Withhold	
 Administer corticosteroids (initial dose of 0.5- 1 mg/kg prednisone or equivalent) followed by taper 	
 Monitor with liver function tests (consider weekly or more frequently until liver enzyme value returned to baseline or is stable)
	Grade 3 or 4	Permanently discontinue	
 Administer corticosteroids (initial dose of 1-2 mg/kg prednisone or equivalent) followed by taper 	

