	Grade 2	Hold until recovery to <2xULN or BL. Restart at same dose level.
	Grade 3 or 4	Hold until recovery to <2xULN or BL. Restart at 1 dose level lower.
AST/ALT Elevation with clinically significant hepatic dysfunction (i.e. total bilirubin ≥ 2xULN excluding biliary obstruction or PT/INR ≥ 1.5xULN)		Permanently discontinue and follow-up per protocol. See Section 5.2.2.3.1 for details in evaluating and managing ALT/AST elevations during axitinib/pembrolizumab combination treatment
Hyperthyroidism	Grades 1-2	Continue at the same dose level
	Grade 3	If symptoms can be controlled with symptomatic medications, or if asymptomatic: may continue at the same dose level or dose reduced by 1 dose level per Investigator judgment
	Grade 4	Hold until recovery to Grade ≤ 1 or BL. Restart at 1 dose level lower.
Hypothyroidism	All grades	Axitinib can be continued while thyroid replacement therapy is instituted
Renal Failure or Nephritis	Grade 1-2	Continue at the same dose level
	Grade 3 -4	Hold until recovery to Grade < 2. Restart at 1 dose level lower.

Toxicity	NCI CTCAE grade	Axitinib
Non-hematologic Toxicities, Laboratory Abnormalities and/or Other Drug Related Toxicities suspected to be contributed to axitinib and not considered immune-related	Grade 1 - 2	Continue axitinib at the same dose level
	Grade 3 - 4	Grade 3 toxicities controlled with symptomatic medications, or Grade 3 asymptomatic biochemistry (other than abnormal liver test) laboratory abnormalities may continue axitinib at the same dose level per Investigator judgment. Other Grade 3 toxicities may continue axitinib dose reduced by 1 dose level. Grade 4 asymptomatic biochemistry laboratory (other than abnormal liver test) abnormality may continue axitinib without interruption per Investigator's judgment. Other Grade 4 non-hematologic/laboratory and non-laboratory abnormalities hold treatment until recovery to Grade <2 then, then restart axitinib dose reduced by 1 dose level.
	Grade 3-4 discontinuation criteria	Permanently discontinue axitinib for: 
 • Severe or Grade 3 drug-related AEs that recur • Any life-threatening AEs. • Subjects with the following events will be permanently discontinued: RPLS, arterial thrombosis/ischemia,
Hematologic Laboratory Abnormalities	Grade 1-3	Continue axitinib at the same dose level.

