
Scenario 4: ALT/AST > 10 × ULN without clinically significant signs of hepatic dysfunction
 
Consultation with Sponsor medical monitor is required prior to rechallenge
	
 • If initial event is likely to be immune-mediated by pembrolizumab: 
 ○ discontinue pembrolizumab and rechallenge with axitinib as monotherapy • If initial event is likely related to axitinib and unlikely due to pembrolizumab: 
 ○ Rechallenge with pembrolizumab monotherapy • If event is potentially related to a contribution of both drugs (such as upfront steroid use with improvement along with axitinib interruption), subject may be rechallenged with axitinib at reduced dose: 
 ○ If no recurrence, continue with axitinib monotherapy ○ If ALT/AST elevation recurs, discontinue axitinib and may be rechallenged with pembrolizumab • Permanently discontinue pembrolizumab if ALT/AST recurrence is >5× ULN or interrupt pembrolizumab if ALT/AST recurrence is >3 to 5× ULN after its rechallenge and manage per Section 5.2.2.1. • Permanently discontinue axitinib if ALT/AST recurrence is >5× ULN or interrupt axitinib if ALT/AST recurrence is >3 to 5× ULN and rechallenge with reduced dose.

Note: 1. Subject should have weekly monitoring with liver tests (i.e., liver enzyme and function tests) for 2-3 weeks after each drug rechallenge. 2. If both study drugs are discontinued due to a hepatic event, subjects should be monitored until AE resolution as per protocol and continue imaging and survival follow-up as per protocol. 3. Events under Scenario 1, 3, and 4 must be reported to the Sponsor as Events of Clinical Interest (see Section 7.2.3.2 for details). 4. Liver tests include liver enzyme (ALT, AST, and ALP) and liver function (bilirubin and PT/INR) tests.
 
Abbreviations: ALP = alkaline phosphatase; ALT = alanine aminotransferase; AST = aspartate aminotransferase; INR = international normalized ratio; PT = prothrombin time.
	

5.2.2.4 Dose Modification Guidelines for Adverse Events Potentially Associated with Sunitinib Treatment

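### For axitinib-attributed ALT/AST above 10xULN without hepatic dysfunction, Tables 8 and 10 give opposite instructions on restarting axitinib, and no text says which governs

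*Combined protocol and SAP*

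**What the plan says.** Section 5.2.2 sets the scope of the dose-modification guidelines: those for a given drug "are to be followed if AEs are assessed as associated or potentially associated with that study treatment". Three tables can then bear on a raised ALT/AST in the combination arm.

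- **Table 8 (Section 5.2.2.2, axitinib).** For Grade 3 or 4 AST/ALT with total bilirubin <2xULN and PT/INR <1.5xULN: "Hold until recovery to <2xULN or BL. Restart at 1 dose level lower". The row has no upper ALT/AST limit. The next row, for elevation with hepatic dysfunction, carries a pointer to Section 5.2.2.3.1 for detail on ALT/AST elevations during combination treatment.
- **Table 10 (Section 5.2.2.3.1, combination).** Scenario 4 covers ALT/AST above 10xULN without hepatic dysfunction and requires consultation with the sponsor's medical monitor before rechallenge. Where the condition is "If initial event is likely related to axitinib and unlikely due to pembrolizumab", the action is "Rechallenge with pembrolizumab monotherapy". Where both drugs may have contributed, axitinib may be tried first at a reduced dose, and then: "If ALT/AST elevation recurs, discontinue axitinib and may be rechallenged with pembrolizumab".
- **Table 6 (Section 5.2.2.1, pembrolizumab).** The row "AST / ALT elevation or Increased bilirubin" reads "Grade 3 or 4 Permanently discontinue". The table is introduced with "Dose modification and toxicity management guidelines for irAEs associated with pembrolizumab are provided in" it, so its stated subject is immune-related events.

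**The concern.** A site facing an ALT/AST above 10xULN with normal bilirubin and PT/INR, which it attributes to axitinib, can open two tables that both fit the event. One leads to axitinib again at a lower level. The other leads to pembrolizumab alone. The protocol treats liver toxicity as a particular risk of this combination: it has its own management section, and ALT/AST above 5xULN in this arm is an Event of Clinical Interest (Section 7.2.3.2).

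The first stake is patient safety. The second is interpretability. Dose modification and discontinuation due to AE are reported endpoints (Section 8.6.2, Table 19), and they would partly reflect which table a site used.

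**Working it through.** The plan states no figure on this point and no arithmetic is needed. The check sets the tables side by side.

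**Do the tables cover the same event?** Table 10 labels ALT/AST above 5xULN as Grade 3 or 4, so above 10xULN falls in the Grade 3 or 4 rows of Tables 6 and 8. Scenarios 2 and 3 define absence of hepatic dysfunction as total bilirubin <2xULN and PT/INR <1.5xULN, the same limits as Table 8's row. Treatment arm does not separate the tables, because axitinib is given only in the combination arm (Table 5).

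**Actions for ALT/AST above 10xULN without hepatic dysfunction:**

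| Attribution | Axitinib, Table 8 | Axitinib, Table 10 | Pembrolizumab, Table 6 | Pembrolizumab, Table 10 | Result |
|---|---|---|---|---|---|
| Axitinib, unlikely pembrolizumab | Hold, restart one level lower | Not restarted | Does not apply | Given alone | Conflict on axitinib |
| Immune-mediated | Not the attributed drug | Given alone | Stopped | Stopped | Agree |
| Both drugs possible | Hold, restart one level lower | Reduced dose | Stopped, if handled as possibly pembrolizumab-associated | Allowed if ALT/AST recurs on axitinib alone | Agree on axitinib at first rechallenge; conditional conflict on pembrolizumab |

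**Neighbouring scenario.** For above 5 to 10xULN attributed to axitinib, Scenario 3 rechallenges axitinib at a reduced dose, in line with Table 8. The break with Table 8 is therefore specific to Scenario 4.

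**Within Scenario 4.** In the both-drugs branch, any recurrence leads to axitinib being discontinued. The last bullet of the same scenario separates two levels: above 5xULN, axitinib is stopped permanently; above 3 to 5xULN, it is interrupted and rechallenged at a reduced dose. For a recurrence of above 3 to 5xULN, the two bullets differ.

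**Precedence.** Table 8's pointer offers detail; it does not say that Table 10 replaces the Grade 3 or 4 row. Table 10 sends the reader to Section 5.2.2.1 for a recurrence after pembrolizumab rechallenge. No text was found that links Table 6 to Table 10 for the initial event.

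**The case against.** The strongest reply has four parts.

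1. **The specific text should govern.** Section 5.2.2.3.1 is written for ALT/AST above 3xULN during combination treatment, and Table 8 sends readers there in words not limited to hepatic dysfunction. Table 8 would keep a role once pembrolizumab has stopped and axitinib continues alone (Section 2.1). This is a reasonable reading, so it would be wrong to say that the protocol gives no direction. Which row the pointer sits in is also weak evidence, since table layout can be lost in text extraction. But the protocol nowhere limits Table 8 to axitinib alone, and a reference for detail is not a statement that one action replaces another.

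2. **The sponsor is consulted anyway.** Scenario 4 requires consultation before rechallenge, ALT/AST above 5xULN in this arm must be reported within 24 hours (Section 7.2.3.2), and rechallenge after a serious event possibly caused by the sponsor's product needs advance approval (Table 15). These safeguards stand and reduce the risk. The gap is that Table 8's row asks for no consultation, so a site working from it alone could restart axitinib without one.

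3. **The pembrolizumab inconsistency is conditional.** In the both-drugs branch, pembrolizumab stays stopped unless ALT/AST recurs on axitinib alone. Section 5.2.2.3.1 treats such a recurrence as further evidence against axitinib. Table 6 is introduced for immune-related events, and the section says that immune-related hepatitis is identified mostly by excluding other causes, axitinib included. This stands: the conflict arises only if the initial event is handled as potentially pembrolizumab-associated under the Section 5.2.2 scope rule. That reading is open, because Scenario 4 describes the event as potentially related to both drugs.

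4. **Severe events in general are not affected.** A reader might infer that the tables disagree on both drugs for any severe elevation. They do not: Scenario 3's axitinib branch agrees with Table 8, and the immune-mediated branches of Scenarios 3 and 4 agree with Table 6.

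**Conclusion.** The point holds in a narrow form. There is one direct contradiction: for ALT/AST above 10xULN, without hepatic dysfunction, attributed to axitinib and not to pembrolizumab, Table 8 restarts axitinib and Table 10 does not. There are two secondary inconsistencies in Scenario 4's both-drugs branch: the conditional one with Table 6 on pembrolizumab, and the one between Scenario 4's own bullets on axitinib after a recurrence of above 3 to 5xULN.

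The frequency is unknown. A reader might infer a size from the Phase 1b figure in Section 5.2.2.3.1, where 4 of 52 subjects (4/52 = 7.7%) had Grade 3 treatment-related ALT/AST elevation or hepatic dysfunction. That figure does not measure the disputed case. It pools all attributions, includes hepatic dysfunction, and does not separate events above 10xULN. Table 3 shows Grade 3 ALT in 2 of 52, Grade 3 AST in none and no Grade 4 for either, and it too gives no count above 10xULN.

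A reader might also infer that sites can act freely on either table. The consultation rule in Scenario 4 argues against that for a site that reaches Table 10. The conclusion rests on the Grade 3 or 4 label in Table 10 and on there being no limiting text in Table 8. It takes no position on which action is clinically right.

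**What to change.** The sponsor's clinical team should:

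- reconcile Table 8's Grade 3 or 4 row with Table 10, Scenario 4, on axitinib, so that one event with one attribution leads to one action;
- align Table 6 and the Scenario 4 bullets for events possibly due to both drugs, covering pembrolizumab after recurrence on axitinib alone and axitinib after a recurrence of above 3 to 5xULN;
- add one sentence in Sections 5.2.2.1 and 5.2.2.2 stating which table governs ALT/AST elevation during combination treatment, and whether the consultation requirement applies whichever table is used;
- notify sites.

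The choice of action belongs to that team. The cost is wording in three tables, the precedence sentence in two sections and a site notice. No hypothesis, endpoint, sample size or analysis method changes. Randomization is complete (N = 861, Section 8.9), so the benefit is to subjects still on combination-arm treatment.

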5. **Decision on axitinib/ pembrolizumab rechallenge** – If initial ALT/AST elevation event is assessed as related to study treatment (*i.e.*, alternative causes were excluded), the decision on rechallenge with one or both study treatments should be based on the outcome of causality assessments (as described above) and the severity of the initial ALT/AST elevation event. Prior to rechallenge with either axitinib or pembrolizumab, initial ALT/AST elevations must recover to $\leq 2 \times$ ULN or to baseline values without signs and symptoms of hepatic dysfunction. See [Table 10](#) for algorithms of decision on axitinib/ pembrolizumab rechallenge after recovery from drug-related ALT/AST elevation.
6. **Severe hepatic events should be promptly managed, including hospital admission and seeking hepatic consultation as appropriate.**

Table 10 Algorithms of decision on axitinib/ pembrolizumab rechallenge after recovery from drug-related ALT/AST elevation

Initial ALT/AST elevation scenario	Rechallenge decision
Scenario 1: ALT/AST > 3 x ULN concurrent with total bilirubin $\geq 2 \times$ ULN (excluding biliary obstruction) and/or PT/INR >1.5xULN (i.e. , ALT/AST elevation with clinically significant signs of hepatic dysfunction)	
 • No rechallenge with either axitinib or pembrolizumab is allowed. Subject should be followed with liver tests until recovery..
Scenario 2: ALT/AST >3-5 x ULN without clinically significant signs of hepatic dysfunction (i.e. total bilirubin < 2xULN and PT/INR <1.5xULN)	
 • Axitinib and pembrolizumab combination can be resumed sequentially with axitinib (at the previous dose) resumed first for 2-3 weeks with weekly liver test monitoring: 
 ○ If no recurrence, consider adding pembrolizumab ○ If with ALT/AST recurrence is >5xULN (i.e., Grade 3 or 4), discontinue axitinib and rechallenge with pembrolizumab ○ If ALT/AST recurrence is >3-5xULN (i.e., Grade 2), dose reduce axitinib then rechallenge or discontinue axitinib and rechallenge with pembrolizumab • Permanently discontinue pembrolizumab if ALT/AST recurrence is >5x ULN or interrupt pembrolizumab if ALT/AST recurrence is >3 to 5x ULN after its rechallenge and manage per Section 5.2.2.1.

Initial ALT/AST elevation scenario	Rechallenge decision

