
Scenario 3: ALT/AST >5 to 10× ULN without clinically significant signs of hepatic dysfunction (i.e., total bilirubin < 2× ULN and PT/INR <1.5× ULN). Consultation with Sponsor medical monitor is required prior to rechallenge.
	
 • If initial event is likely to be immune-mediated by pembrolizumab (i.e., no prompt decrease in ALT/AST after axitinib interruption and required initiation of steroid treatment as described in item 3b of this section, responded to steroid treatment, and no alternative explanations): 
 ○ discontinue pembrolizumab and rechallenge with axitinib as monotherapy (at same dose) • If initial event is likely related to axitinib (e.g. prompt recovery after axitinib interruption without confounding by steroid treatment), first rechallenge with axitinib (at reduced dose) for 2 to 3 weeks with weekly liver test monitoring: 
 ○ If no recurrence, add pembrolizumab ○ If ALT/AST recurrence is >5× ULN, permanently discontinue axitinib and rechallenge with pembrolizumab ○ If ALT/AST recurrence is >3 to 5× ULN, dose reduce axitinib then rechallenge or discontinue axitinib, depending on the reoccurrence of the events and rechallenge with pembrolizumab • Permanently discontinue pembrolizumab if ALT/AST recurrence is >5× ULN or interrupt pembrolizumab if ALT/AST recurrence is >3 to 5× ULN after its rechallenge and manage per Section 5.2.2.1.

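### Table 10, Scenario 4, both-drugs branch only: an ALT/AST recurrence of >3 to 5×ULN on rechallenged axitinib meets two conflicting instructions

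*Combined protocol and SAP*

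**What the plan says.** Table 10 in protocol Section 5.2.2.3.1 sets out how axitinib and pembrolizumab may be given again after a drug-related ALT/AST elevation has recovered. Scenario 4 is entered with "ALT/AST > 10 × ULN without clinically significant signs of hepatic dysfunction". The row requires the sponsor's medical monitor to be consulted before rechallenge. It then has three branches by attribution:

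- Event likely immune-mediated: "discontinue pembrolizumab and rechallenge with axitinib as monotherapy". This branch has no recurrence rule of its own.
- Event likely due to axitinib and unlikely due to pembrolizumab: rechallenge with pembrolizumab alone.
- Both drugs potentially contributing: "subject may be rechallenged with axitinib at reduced dose". With no recurrence, axitinib continues alone. Otherwise, "If ALT/AST elevation recurs, discontinue axitinib and may be rechallenged with pembrolizumab".

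Two further bullets close the cell at the outer level, neither tied to a branch. One deals with recurrence after pembrolizumab rechallenge. The other deals with axitinib: "Permanently discontinue axitinib if ALT/AST recurrence is >5× ULN", or "interrupt axitinib if ALT/AST recurrence is >3 to 5× ULN and rechallenge with reduced dose".

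**The concern.** The sub-bullet in the both-drugs branch applies to a recurrence of any size. The closing axitinib bullet applies to any subject in Scenario 4 who has been rechallenged with axitinib. A both-drugs subject with a recurrence of >3 to 5×ULN satisfies both conditions, and the two actions differ: axitinib is stopped with a possible move to pembrolizumab, or axitinib is paused and given again.

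These subjects have already had a liver event above 10×ULN and a second elevation on re-exposure. Whether they receive axitinib a further time should follow from the protocol, and should not turn on which of two lines is consulted. The instruction is still live. Randomization is complete (N = 861, Section 8.9), but axitinib continues until progression is verified or confirmed (Section 2.1).

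**Working it through.** The plan states no figure on this point and no arithmetic applies. The check sets the bullets side by side.

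**1. Each branch of Scenario 4 against each recurrence band on axitinib**

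| Branch | Recurrence >3 to 5×ULN | Recurrence >5×ULN |
|---|---|---|
| Immune-mediated | Only the closing bullet applies: interrupt, then reduced-dose rechallenge. No conflict. | Only the closing bullet applies: permanent stop. No conflict. |
| Axitinib-related | Axitinib is not rechallenged, so the case does not arise. | Does not arise. |
| Both drugs | Sub-bullet: discontinue axitinib, possibly rechallenge with pembrolizumab. Closing bullet: interrupt axitinib and rechallenge with it. **Conflict.** | Both bullets stop axitinib. No conflict. |

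The conflict therefore occupies one cell: the both-drugs branch in the >3 to 5×ULN band.

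**2. How the neighbouring scenarios treat the same band**

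- Scenario 2: "dose reduce axitinib then rechallenge or discontinue axitinib and rechallenge with pembrolizumab".
- Scenario 3: "dose reduce axitinib then rechallenge or discontinue axitinib, depending on the reoccurrence of the events".

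Both name the two actions in one bullet as explicit alternatives. Scenario 4 puts them in separate bullets at different levels, with no such link and no order of precedence.

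**3. Can the closing bullet be carried out in the both-drugs branch?**

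The subject is already on a reduced axitinib dose there, so one might think a further reduction is excluded. Table 9 lists two levels below the starting dose (3 mg and 2 mg BID). The axitinib-related branch of Scenario 3 also starts rechallenge at a reduced dose and still allows a further reduction on recurrence. The closing bullet is therefore feasible in this branch and cannot be set aside as impossible.

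**The case against.** The strongest reply is that the specific line governs the general one. The sub-bullet is nested in the both-drugs branch. The closing bullet is general, and it supplies a recurrence rule that the immune-mediated branch lacks. On that reading the defect is an unstated scope. The reading is plausible, but the text does not compel it: the closing bullet is limited to no branch and, as shown, can be applied in this one.

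A second reply is that the sub-bullet does not call the stop permanent, unlike wording used elsewhere in the cell, so axitinib might be resumed. But the sub-bullet pairs the stop with a possible move to pembrolizumab and says nothing of a return to axitinib. If a temporary stop is meant, that too needs stating.

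A third reply is supervision, and much of it stands. The Scenario 4 row requires consultation with the medical monitor before rechallenge, and both disputed next steps are rechallenges. Table 15 (Section 7.2.4) requires advance sponsor approval of rechallenge after a serious event that the product may have caused, or where re-exposure adds significant risk. Section 5.2.2.3.1 requires both drugs to be interrupted above 3×ULN and recovery to at most 2×ULN or baseline before rechallenge. Note 1 to Table 10 adds weekly liver tests for 2 to 3 weeks after each rechallenge. A site does not decide alone, and a reader who inferred that would go too far. These safeguards lower the risk. They do not say which bullet applies, and the monitor has the same two to read.

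**Conclusion.** The point holds for one branch and one band: Scenario 4, both drugs contributing, recurrence on axitinib of >3 to 5×ULN. It rests on reading the closing bullet as written, without a limit to any branch.

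Three stronger readings are not supported:

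- A reader might infer that Scenario 4 as a whole contradicts itself. It does not: the other two branches are consistent, and above 5×ULN so is this one.
- A reader might size the problem from the 4 of 52 earlier-study subjects with Grade 3 events in Section 5.2.2.3.1: 4/52 = 7.7%, or about 33 of roughly 430 combination subjects (861/2). That count covers Grade 3 treatment-related ALT/AST elevation or hepatic dysfunction. It does not isolate events above 10×ULN, and raised ALT/AST with dysfunction can fall under Scenario 1. Table 3, from the same 52-subject study, shows Grade 3 ALT in 2 of 52, Grade 3 AST in none, and no Grade 4 of either. To reach the conflict a subject must also be attributed to both drugs, recover, be given axitinib again and recur within the band. The documents give no rate for these steps, so the number cannot be stated beyond saying that it is probably small.
- A reader might infer an effect on the treatment comparison. PFS and OS are analysed by intention to treat, and the primary PFS censoring rules do not use treatment discontinuation. Only PFS Sensitivity Analysis 2 does (Table 16). Discontinuation due to an AE is a descriptive Tier 3 item (Table 19). No confirmatory efficacy result is affected.

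What remains is a verifiable inconsistency in a hepatic safety rule. It matters for subject safety and consistent conduct and should be corrected.

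**What to change.** Reconcile the both-drugs sub-bullet and the closing axitinib bullet of Scenario 4 by stating which branch and which recurrence band each covers. If the closing bullet is meant for one branch only, say so there. If both actions are meant as alternatives, put them in one bullet, as Scenarios 2 and 3 do. State also whether the stop in the sub-bullet is permanent. Which instruction applies is a decision for the sponsor's clinical team, and this review takes no position on it.

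The cost is about one line of Table 10. No endpoint, sample size or analysis changes.
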